22.2 Severity Classification

The severity of an event is evaluated in order to subcategorize events. Severity is *not* seriousness. A very severe event can be non-serious, and a serious event can be of mild severity. All AEs (including SAEs) are to be recorded on the AE page of the subject's eCRF. Each event will be graded for severity using Common Terminology Criteria for Adverse Events (CTCAE), v4.03 grading scale: June 14, 2010.

The following grading will apply:

- Mild (Grade 1) Mild; asymptomatic or mild symptoms; clinical or diagnostic observations only; intervention not indicated.
- Moderate (Grade 2) Moderate; minimal, local, or non-invasive intervention indicated; limiting ageappropriate instrumental Activity of Daily Living (ADL).

Protocol Code Number: SynAct-CS002

- Severe (Grade 3) Severe or medically significant but not immediately life-threatening; hospitalization or prolongation of hospitalization indicated; disabling; limiting self-care ADL.
- Life-threatening (Grade 4) Life-threatening consequences; urgent intervention indicated.
- Death (Grade 5) related to AE.

22.3 Relationship to Study Drug

A determination will be made of the relationship (if any) between an adverse event and the study drug. A causal relationship is present if a determination is made that there is a reasonable possibility that the adverse event may have been caused by the study drug.

The investigator should determine the relationship of an AE to the study drug after thorough consideration of all facts that are available and will be assessed using the following definitions:

- **Definitely not related**: Temporal relationship to study drug administration is missing or implausible, or there is an evident other cause
- **Probably not related**: Temporal relationship to study drug administration makes a causal relationship improbable; and other drugs, chemicals, or underlying disease provide plausible explanations
- **Possibly related**: The AE occurred in a reasonable time after study drug administration but could be related to an underlying disease, environmental or toxic factors, or other drug or therapy
- **Probably related**: Reasonable time sequence to the administration of study drug and unlikely to be attributed to concurrent disease or the drugs or chemicals, and which follows a clinically reasonable response on withdrawal (dechallenge). Rechallenge information is not required
- **Definitely related**: Plausible time relationship to study drug administration and event cannot be explained by concurrent disease or other drugs or chemicals. The response to withdrawal of the drug (dechallenge) should be clinically plausible. The event must be definitive pharmacologically or phenomenologically, using a satisfactory rechallenge procedure if necessary

22.4 Reporting Procedures of Adverse Events

The responsible for ensuring that all AEs (as defined in Section 18.1) observed by the staff at the clinic or reported by subjects are collected and recorded in the subject's medical notes and the eCRF. The condition of each subject will be monitored throughout the study.

All AEs will be reported starting from the time informed consent for study participation is provided and until the final visit (End of Study/Early Termination visit) has occurred. All AEs that are ongoing at the subject's last visit must be followed until resolution or for 4 weeks after the study drug administration, whichever comes first.

A cluster of signs and symptoms that results from a single cause should be reported as a single AE (e.g., fever, elevated WBC, cough, abnormal check x-ray, etc. can all be reported as Pneumonia). The investigator must assign the following adverse event attributes: adverse event diagnosis or syndrome(s) (if known, signs or symptoms if not known); dates of onset and resolution; severity; assessment of relatedness to investigational product and action taken.

Protocol Code Number: SynAct-CS002

22.5 Reporting Procedures for Serious Adverse Events

All SAE reporting start at the time the subject has been administered the first dose of study drug and until end of study visit. Ongoing SAEs must be followed until the event resolves, or the event sequelae stabilize, or it is unlikely that any additional information can be obtained.

In the event of an SAE, the investigator must:

- Complete the provided SAE report Form with the following information, as a minimum:
 - valid EudraCT number,
 - o sponsor study number,
 - one identifiable coded subject,
 - o one identifiable reporter,
 - o one SUSAR,
 - o one suspect IMP (including active substance name-code),
 - A causality assessment.
- All SAEs are to be reported to the sponsor (or designee) within 24 hours of awareness of the event. Send
 it to:
 - PharmaLex contact information: [contact]
- Obtain and maintain in the subject's medical record all pertinent medical records, information, and medical judgments from colleagues, who assisted in the treatment and follow-up of the subject.
- Provide PharmaLex with additional information that may become available using the SAE reporting form. All documents submitted to PharmaLex that contains information regarding the SAE must be redacted (blacked out) for protected confidential health information, including subject initials. The assigned subject screening number should instead be recorded on each of the documents.

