21.1.9.7 Safety (AE and SAE)

Safety measures (AEs, SAEs, including laboratory abnormalities) will be registered during the whole study duration.

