22 SAFETY

Adverse events will be monitored from the time that the subject gives informed consent and throughout the study, and will be elicited by direct, non-leading questioning or by spontaneous reports. Further details for AE reporting can be found in section 18.4.

Conditions that started before signing the informed consent and for which no symptoms or treatment are present until the first administration of study drug (e.g., seasonal allergy without acute complaints), are recorded as medical/surgical history.

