22.1 Definitions

Adverse Events (AE): According to the International Conference of Harmonization (ICH), an AE is any untoward medical occurrence in a subject or clinical investigation subject administered a pharmaceutical product and which does not necessarily have a causal relationship with this treatment.

An AE can therefore be any unfavorable and unintended sign (including an abnormal laboratory finding), symptom, or disease temporally associated with the use of a medicinal or investigational product, whether or not considered related to the medicinal or investigational product. Pre-existing conditions which worsen during a study are to be reported as AEs.

Adverse Reaction (AR): All untoward and unintended responses to an investigational medicinal product related to any dose administered.

Serious Adverse Events (SAE): An SAE is any AE occurring at any dose that in the view of either the investigator or sponsor, results in any of the following outcomes:

Protocol Code Number: SynAct-CS002

- Results in death, or
- Is life threatening, that is any event that places the patient at immediate risk of death from the event as it occurred. It does not include an event that, had it occurred in a more severe form, might have caused death, or
- Requires inpatient hospitalization or prolongation of existing hospitalization, or
- Results in persistent or significant disability/incapacity, or
- Is a congenital anomaly/birth defect

Important medical events that may not result in death, be life-threatening, or require hospitalization may be considered a serious adverse event when, based upon appropriate medical judgment, they may jeopardize the subject and may require medical or surgical intervention to prevent one of the outcomes listed in this definition.

- Hospitalization is defined as any in-patient admission (more than 24 hours).
- Prolongation of hospitalization is defined as any extension of an in-patient hospitalization beyond the stay
 anticipated/required in relation to the original reason for the initial admission, as determined by the
 investigator or treating physician. Prolongation in the absence of a precipitating, treatment-emergent,
 clinical AE (i.e., not associated with the development of a new AE or worsening of a pre-existing condition)
 may meet criteria for "seriousness" but is not an adverse experience and thus is not subject to immediate
 reporting.

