| Phase of study at time of event (SAESP)                                       | # patients and % /category (4 categories:
Screening/Treatment/Wash-out/Follow-up),
included in SAE table   |
| Study Drug Information (SAESD, SAEFREQ, SAEFADT, SAELADT)                     | Listing only   |
| SAE abate after stopping study medication (SAEDECH)                           | Listing only   |
| SAE reappear after reintroduction of study medication (SAERECH)               | Listing only   |
| Blinding code broken (SAEBBROK, SAEBBDT)                                      | Listing only   |
| Concomitant medication (SAECM)  | Listing only   |
| Relevant medical history (SAEMH)  | Listing only   |
| Hospitalisation Details (SAEHOSP, SAEADT, SAEDDT)                             | Listing only   |
| Death Details (SAEDEDT, SAEPCAUS, SAEAUTO, SAEINF)                            | Listing only   |

The incidence of AEs will be summarized by the reported AE term. A subject will be counted only once in the incidence count for a specific AE term, although an AE term might be reported more than once for a particular subject.

Separate summaries will be provided for relationship (yes, no) to study drug. An AE will be considered related to study drug if the investigator reported the event to be "definitely, probably, possibly, or unlikely" related to treatment on the CRF.

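### Protocol 22.5 starts SAE reporting at first dose while other sections start collection at consent, so serious pre-dose events have no consistent route to the sponsor

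*Protocol*

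**What the plan says.** Protocol 22.5 sets the window for serious events: "All SAE reporting start at the time the subject has been administered the first dose of study drug", and it closes at the end of study visit. The same section contains the SAE report form and the 24-hour limit for telling the sponsor.

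Other current text starts earlier or has no such limit:

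- Protocol 22: "Adverse events will be monitored from the time that the subject gives informed consent and throughout the study".
- Protocol 22.4: "All AEs will be reported starting from the time informed consent for study participation is provided".
- Protocol 21.1.9.7: "Safety measures (AEs, SAEs, including laboratory abnormalities) will be registered during the whole study duration".
- Protocol 22.2: "All AEs (including SAEs) are to be recorded on the AE page of the subject's eCRF".
- SAP 7.10 summarises the study phase of each SAE in four categories, "Screening/Treatment/Wash-out/Follow-up".

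The visit schedule is a third variant. In protocol Table 3 the row for SAEs and AEs is first marked at Visit 2 (Baseline), and the Visit 1 list in 20.1.1 has no adverse event item. The Visit 2 list in 20.1.2 does have one.

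**The concern.** A serious event is a kind of adverse event. A site that meets one after consent but before dosing reads in 22.4 that it is reportable and in 22.5 that SAE reporting has not yet begun. Two sites could follow the text in good faith and act differently: one sends the SAE form within 24 hours, the other only enters the event in the notes and the eCRF. Section 22.4 sets no time limit for informing the sponsor, so following it does not replace the 22.5 route.

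Screening is not free of study requirements. It involves study blood sampling (36 mL in Table 6) and X-rays unless recent films exist, and corticosteroids are prohibited from two weeks before screening. The sponsor has reason to want serious events in this period handled uniformly.

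There is a related gap in the SAP. AEs are collected from consent, but SAP 7.10 gives no rule separating events that began before dosing from treatment-emergent ones.

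**Working it through.** No sample size, power or event count is involved. The check compares the stated windows and then measures the gap.

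**Windows side by side, for a serious event after consent and before first dose**

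| Source | Covers the event? |
|---|---|
| Protocol 22, AE monitoring | Yes, from consent |
| Protocol 22.4, AE reporting in notes and eCRF | Yes, from consent |
| Protocol 22.2, eCRF AE page | Yes, SAEs included; no start point given |
| Protocol 21.1.9.7, registration | Yes, whole study; SAEs named |
| Protocol 22.5, SAE form and 24-hour report | No, starts at first dose |
| Table 3 and 20.1.1, Visit 1 | Nothing scheduled |
| Table 3 and 20.1.2, Visit 2 | Yes, if the subject attends Baseline |
| SAP 7.10, SAE phase | Yes, a screening category exists |

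Recording is therefore required. What 22.5 withholds before dosing is the SAE form and the 24-hour report.

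**Length of the gap.** The synopsis gives screening of up to 2 weeks, 4 weeks of dosing and 4 weeks of safety follow-up.

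- Total: 2 + 4 + 4 = 10 weeks, which reproduces the stated participation time.
- Longest screening: 14 / (14 + 28 + 28) = 14/70 = 20%.
- Shortest screening in Table 3 (1 day): 1 / (1 + 28 + 28) = 1/57 ≈ 1.8%.

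**Who is affected.** Planned enrolment is up to 120 + 60 = 180 subjects (protocol 15.1). Those who attend Baseline are asked about events there. Screen failures who never attend have only the general text of sections 21.1.9.7, 22, 22.2 and 22.4. Neither document gives an expected number of screen failures or a pre-dose event rate, so no event count can be derived.

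**Reach into the analysis.** SAP 3.2 defines the safety set as subjects dosed at least once, and SAP 7 keeps undosed patients out of the frequency tables. An SAE in a screen failure is outside those tables whichever start point applies. A pre-dose event in a subject who is later dosed can enter the by-treatment AE summary. SAP 7.10 counts each subject once per reported term and sets no condition on onset relative to first dose.

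**The case against.** The strongest defence is that the sections govern two different channels: 22.4 covers recording in notes and eCRF, 22.5 covers expedited reporting. A site can obey both by recording from consent and expediting from first dose. The definitions give some support. Section 22.1 reads "An SAE is any AE occurring at any dose that in the view of either the investigator or sponsor", and the minimum content of the SAE form includes a suspect IMP and a causality assessment, which fit a dosed subject. A first-dose start may be deliberate. Section 26.1 also provides for SAE reporting to ethics committees and authorities under local rules, with no tie to first dose.

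This stands as a reason not to presume which start point the sponsor wants. It does not remove the inconsistency. Nothing in 22.4 or 21.1.9.7 says that serious events are handled differently before dosing, and the SAP expects some in the screening phase. If first dose is intended, those passages need an exception.

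Three stronger readings are tempting, and the documents do not support them:

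- A reader might infer that serious events in screening go unreported altogether. Sections 21.1.9.7, 22.2 and 22.4 still require them to be recorded, and Baseline collects them from subjects who attend.
- A reader might infer that the SAP screening row will be zero by rule. The phase variable is listed among SAE-specific fields, which may suggest that it comes from the SAE form, but neither document says it is completed only after a 24-hour report.
- A reader might infer that the primary safety comparison is materially distorted. Pre-dose events carry no information about AP1189 against placebo, and undosed subjects are excluded from the tables.

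It is also fair to say that the SAP already offers partial separation, by SAE phase and by visit. That does not extend to the overall incidence by AE term.

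**Conclusion.** The inconsistency is real and lies in current text. Its supported consequence is narrow: serious events between consent and first dose must be recorded, but on a literal reading of 22.5 they fall outside the SAE form and the 24-hour report. Sites may therefore differ, and the gap is clearest for screen failures who never reach Baseline.

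The affected window is up to about 2 of 10 weeks per subject. The 20% assumes that screening uses its full two weeks; it is a share of time, not of events. Events are probably few, which is a judgement rather than a figure from the documents. The effect on the treatment comparison is small. The point is worth correcting because it changes what sites send to the sponsor and costs very little.

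**What to change.** 1. State one SAE start point and make protocol 21.1.9.7, 22, 22.4, 22.5, Table 3 and SAP 7.10 agree with it. The choice is the sponsor's. Most of these passages point to consent, while the definition in 22.1 and the suspect-IMP item on the form fit first dose.
2. If consent is chosen, say explicitly how serious events in screen failures are captured, and adapt the form items that presuppose dosing. A Visit 1 mark in Table 3 is not enough: consent is signed at that visit, so the mark would catch little beyond same-day events.
3. If first dose is chosen, write the exception for serious events into 21.1.9.7, 22 and 22.4, and explain what the screening category in SAP 7.10 is meant to hold.
4. Under either choice, tabulate events with onset before first dose separately from treatment-emergent events in SAP 7.10, so that by-treatment AE incidence does not mix in pre-dose events. The data exist: AE start date is collected and the diary records dosing date and time. Since SAP 7.10 lists no AE start time, a convention is needed for events that begin on the day of first dose.

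The cost is a few sentences in the protocol, one rule and one table split in the SAP, and, if consent is chosen, a few more SAE reports.

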22.6 Reporting of SAE and SUSAR to the Competent Authorities

In the event of a fatal and life-threatening SUSAR, the sponsor should report at least a minimum of information to the CA, IECs/IRBs no later than 7 days after being made aware of the event. SUSARs which are not fatal and not life-threatening are to be reported within 15 days of awareness. When/if follow up information becomes available, this should be submitted to the authorities within 15 days of receipt.

PharmaLex should compile and submit listings of all SARs in a Development Safety Update Report (DSUR) to the CA, IECs/IRBs once a year, as applicable.

22.7 Expedited Reporting

The sponsor will ensure that processes are in place for submission of reports of Suspected Unexpected Serious Adverse Reactions (SUSARs) occurring during the study to the CA, IECs/IRBs and other investigators concerned by study drug. Reporting will be done in accordance with the applicable regulatory requirements.

Protocol Code Number: SynAct-CS002

22.8 Contraception and Pregnancy

The effects of AP1189 on a fetus during pregnancy are unknown. Therefore, women who are of childbearing potential should use one of the below contraceptive methods which, when used consistently and correctly are considered as highly effective birth control methods. Contraception must be used during the study and two weeks after the last IMP has been taken (equal to 5 times T1/2).

Highly effective birth control methods to be used during the study:

Oral contraceptives, implant, transdermal patch contraceptives, injection contraceptives, intravaginal contraceptive ring, and intrauterine device (IUD) or depot injection.

Sterile or non-fertile subjects are exempt from the requirement for contraception. To be considered sterile or non-fertile, one should generally be surgically sterilized (vasectomy / bilateral tubectomy, hysterectomy and bilateral ovariectomy) or be postmenopausal, defined as missed menstruation for at least 12 months prior to enrollment in the study.

In addition, true abstinence (total abstinence from heterosexual intercourse) when this is in line with the preferred and usual lifestyle of the subject.

At all visits, subjects should be reminded of the importance of maintaining contraception and avoiding pregnancy during the study.

Subjects with a positive pregnancy result prior to baseline (Day 0) will not be eligible to participate in the study. If a female subject becomes pregnant during the treatment period of the study, she must stop taking the study medication and immediately inform the investigator. The investigator should report all pregnancies within 24 hours to PharmaLex on an SAE report Form provided. The investigator should counsel the subject and discuss the risks of continuing with the pregnancy and the possible effects on the fetus. Monitoring of the subject should continue until the conclusion of the pregnancy. Information regarding a pregnancy occurrence in a study subject and the outcome of the pregnancy will be collected.

Male subjects: Either the partner uses one of the above safe methods or the subject and his partner use double barrier meaning condom in combination with a diaphragm. Male subjects must inform their partner(s) of the risks of becoming pregnant and for reporting any pregnancy to the study doctor.

22.8.1 Additional Reporting Requirements for Pregnancies

If a female subject of childbearing potential becomes pregnant during the study, the coordinating investigator will immediately notify the sponsor, within 24 hours of being made aware of the event. Complete the provided Pregnancy Report Form and send it to:

PharmaLex (or designee) contact information: [contact]

The investigator should follow any subject who becomes pregnant, while participating in a clinical study, throughout the pregnancy. The investigator should document the outcome of the pregnancy and provide a copy of the documentation to the PharmaLex.

23 STATISTICAL CONSIDERATIONS AND METHODS

Protocol Code Number: SynAct-CS002

23.1 General Considerations

Before breaking the treatment codes, all decisions on the evaluability of the data from each individual subject will be made and documented, and each subject will be assigned to the appropriate analysis data set. The following analysis sets will be used for the statistical analysis:

Safety: All subjects who received the study medication at least once, analyzed by received

treatment

PK: All the subjects who completed the study and did not have any protocol deviation or events

implying a bias for the PK evaluation

Efficacy: All randomized subjects who received the study medication at least once, analyzed by

randomized treatment (intention to treat). A second analysis of the primary efficacy endpoint, for robustness, will be performed for all randomized subjects who complete the

study without any major protocol violations (per protocol)

A Statistical Analysis Plan (SAP) describing the planned statistical analyses in detail, including interim analyses, will be prepared by CroxxMed, and validated by the sponsor prior to any unblinding of data.

23.2 Determination of Sample Size

Calculations of sample size are based on a 95% confidence interval for the mean change in CDAI from baseline.

23.2.1 Main study

For a sample size of 25 subjects, and a standard deviation for the mean change of 3 points, a 95% confidence interval will be around 2.8 points wide with 80% probability. This interval width provides a good precision of the estimate of the primary efficacy endpoint. For a sample size of 30 subjects, the interval will be around 2.5 points wide, which provides even better precision. If the sample size is larger, or if the standard deviation is smaller, the interval will be shorter (i.e., the precision will be higher). A larger standard deviation than 3 points is unlikely. SAS proc power is used for the calculations.

The study is designed to provide a minimum of 30 subjects in each of the treatment groups that proceed to Part 2, and a total of 90 patients.

